**Testing Products to Increase Children's Physical Activity in the Classroom: Identifying
What Works and What Doesn't**

Identifiers:NCT03394846 Unique Protocol ID: Pro00069012

5/26/2022

Study setting and participants

Study protocols were approved by the [REDACTED] IRB prior to enrollment of the first participant. Data were collected from five elementary schools in two separate school districts. Both school districts served a major metropolitan area in one southeastern state in the United States. Table 1 presents the participating schools' characteristics. These schools were identified to participate because they served a large number of minoritized children from families that are low income. These students often experience disproportionately fewer opportunities to participate in PA [18]. At regularly scheduled faculty meetings, teachers in the participating schools were provided with information about the study and invited to participate. Teachers who agreed to participate were provided with and signed an informed consent form. A total of 57 (60%) of teachers consented. For students in the consented teachers' classes, a passive consent procedure was employed due to the noninvasive and low-risk nature of the study. Letters with information about the study were sent home to the parents of children in the participating classes. If a parent did not wish for their child to participate, the letter informed them to sign and return the form to their child's classroom teacher. A total of 123 (5.2%) parents opted out of their child wearing the activity monitor. Prior to data collection, all children provided verbal assent.

Study design/procedure

The COVID-19 pandemic impacted this study and caused changes to the design. Prior to the COVID-19 pandemic, this pre-post study was designed to assess teachers' intact classrooms for a total of five weeks, at two separate timepoints in the spring (i.e., January and February) and fall (September and October) of 2020. The intention was to provide all teachers with three MI products to test in their classroom for one week each. The teachers would also be observed for

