one week (i.e., baseline) when they were asked to go about their regularly scheduled classroom activities like any other typical week. The decision was made not to include a comparison group of teachers based on feedback from school administrators indicating they desired all participating teachers to receive a MI product and would not participate if that was not the case. One baseline week was allocated for the spring and fall. Following the baseline week, teachers were to receive one MI product to use (i.e., intervention). Teachers were to try one MI product in the spring and two products in the fall. The order of product testing was counterbalanced at the school level to minimize contamination and potential timing effects. However, due to disruptions of the COVID-19 pandemic, the study was not able to be executed as designed, and the provision of the MI products and measures were not completed in the fall of 2020. Thus, we collected one baseline week and one intervention week in spring of 2020, prior to the onset of the COVID-19 pandemic related school closures. This meant that each school only received one MI product for testing (see Table 1 for the product that each school tested).

The intention of this study was to maximize ecological validity [19]. Therefore, to simulate off-the-shelf conditions, no orientation or training related to MI product implementation was provided by the study team. Associated product orientation materials were provided to the teachers to review at their discretion one week prior to the intervention week. Teachers were allowed to determine the times and duration of product use and there were no restrictions or guidance from the research team. Teachers were informed that they were free to use any feature of the product to implement in their classroom as often or infrequently as they preferred. All teachers were informed of the study's purpose and that the study staff were not affiliated with the MI products. The three MI products were selected for this study because in a previous product

testing study conducted by our research team [20], teachers rated these products the highest and indicated that these products maximized facilitators of use while minimizing barriers to use.

Sample Size Considerations

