For each day that teachers participated in the study, they were asked to complete a daily log at the end of the school day indicating total uses of MI strategies (e.g., use of any MI product, provided or otherwise), uses of the specific MI product that they were provided, and the amount of time they used these products/strategies. In addition to use of the MI product, teachers were asked to provide information about their daily classroom schedule and out of classroom activities (e.g., physical education, recess, Art/Music, lunch). The log was collected from the teacher daily at the end of the school day by a trained research assistant.

Sedentary behaviors and Physical Activity.

Each teacher was observed on five school days during baseline and intervention weeks. In classrooms with 20 students or fewer (n=34) all students received an accelerometer. In classrooms with more than 20 students (n=23, mean number of students=24, SD=1.4) the first 20 students to arrive to school received an accelerometer each observation day. Random selection of students in classes with more than 20 students was not deemed necessary for because, this study focused on classroom level estimates of SB and PA, and classrooms with more than 20 students had a mean of 24 (SD=1.4) students. Thus, the vast majority of students were measured on any

given day. At the end of the school day, accelerometers were collected by trained research staff. Accelerometers (ActiGraph GT3X+ Shalimar, FL) were affixed to students' non-dominant wrist. Students' engagement in SB, light PA (LPA), and moderate-to-vigorous PA (MVPA) were calculated using previously developed cutpoint thresholds for elementary age children's sedentary behavior, LPA and MVPA [23]. Accelerometer epochs were set to five seconds to account for the intermittent and transitory nature of youth PA [24]. A valid day of accelerometer wear was defined as total time in attendance of at least 70% of the school day (260 mins) [25]. Age, sex, and race of all students were collected using school records.

Statistical analyses

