Analyses were conducted on children that had at least one accelerometer wear day [26-28]. Descriptive means, standard deviations, and percentages (for dichotomous variables) were calculated for demographic characteristics, SB and PA, and teacher MI uses. Mixed effects general linear models were used to evaluate the impact of providing teachers access to MI products on their MI strategy use. Days measured were nested within teachers, and teachers were nested within schools. The dependent variables were number of overall MI strategy uses/day, the amount of time implementing MI per day, and the number MI product uses/day for the specific product provided. The independent variable was a dichotomous baseline or intervention week variable. To evaluate the impact of providing teacher access with MI products on students' SB and PA, mixed effects general linear models were estimated with days measured nested within children, children, nested within teachers, and teachers nested within schools. Separate models were estimated with SB, LPA, and MVPA as the dependent variables and the dichotomous baseline or intervention week variable as the independent variable. PA models controlled for

children's age (years), race, sex, and time in attendance at school. Additionally, all analytic models controlled for school day level factors (i.e., physical education vs. non-physical education day, recess vs. non-recess day).

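### The week-effect models name no teacher-by-week or school-by-week term, so their intervals are too narrow if teachers or schools change by different amounts.

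*Combined protocol and SAP*

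**What the plan says.** Under Study setting and participants: "Data were collected from five elementary schools in two separate school districts", and "A total of 57 (60%) of teachers consented".

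Under Study design/procedure, the design as executed is pre-post with no comparison group: "Thus, we collected one baseline week and one intervention week in spring of 2020". School determined the product: "This meant that each school only received one MI product for testing". Under Outcomes: "Each teacher was observed on five school days during baseline and intervention weeks". I read this as five days in each week.

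Under Statistical analyses, the teacher models are mixed effects general linear models. For the clustering: "Days measured were nested within teachers, and teachers were nested within schools". For the exposure: "The independent variable was a dichotomous baseline or intervention week variable". The student models for sedentary behaviour, light activity and moderate-to-vigorous activity add children as a level between days and teachers and use the same week indicator. All models adjust for physical education days and recess days, and the activity models also adjust for child covariates and attendance time. No teacher-by-week, school-by-week or product term is named, and the text does not say whether the random effects are intercepts only.

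**The concern.** Listing teacher and school as nesting levels looks like full allowance for clustering. For a contrast between two weeks measured on the same teachers, it may not be. A teacher or school intercept describes how high that unit sits in both weeks, and it drops out of the difference. What matters for the week effect is how much the change varies from teacher to teacher and from school to school. The section names no term for that.

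Such variation is plausible here. Teachers chose when, how long and how often to use the product. Each school used a single product, and with one week either side, any school-wide event in either week enters the change of all its teachers. If the variation exists and is not modelled, the intervals for every week effect are too short. That includes minutes of movement integration (MI) per day, the outcome in which the sample size is expressed.

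**Working it through.** **The plan's own figure.** Sample Size Considerations states 60 teachers, power 0.8, alpha 0.05 and a detectable effect of 0.32, or 8.3 minutes (implied SD 8.3/0.32 = 25.9 minutes). A paired t-test on 60 independent teacher changes gives power 0.790 at 0.32 one-sided and 0.684 two-sided. The figure is therefore matched, to within rounding, by a one-sided paired test with teachers independent. The section mentions no school clustering.

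**Inputs.** From the documents: 57 teachers, 5 schools (57/5 = 11.4 teachers per school on average) and 5 days in each week. Assumed: near-equal school sizes (11/11/11/12/12), a Gaussian outcome, day residual variance set to 1, no missing days. Also assumed, because the documents give neither: the school-by-week variance vS and the teacher-by-week variance vT, both relative to the day variance.

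**Step 1: what the intercept-only model estimates.** A teacher's change is the difference of two five-day means, so its day-level variance is 2/5 = 0.4. The week effect is the mean of 57 changes. The true and reported variances are:

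- True: (0.4 + vT + 11.4 vS)/57.
- Reported: 0.4 s²/57. Here s² pools 57 × 8 = 456 within-week df with the spread of teacher changes, on 57 × 9 − 1 = 512 df. Its expectation is {456 + 2.5 × [56(0.4 + vT) + 45.6 vS]}/512, with 45.6 = 57 − 11.4.

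The 456 within-week df carry no information on how changes vary, so s² barely moves when changes differ.

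**Step 2: schools differ, teachers within a school do not (vT = 0).** With ICC = vS/(vS + 0.4), an ICC of 0.05 gives vS = 0.0211. The true numerator is 0.4 + 11.4 × 0.0211 = 0.640. The reported numerator is 0.4 × 1.005 = 0.402. The SE is too small by √(0.640/0.402) = 1.26, and the false-positive rate is 2[1 − Φ(1.96/1.26)] = 12.0%. Results over the range:

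| Assumed ICC of change within school | SE too small by a factor of | False positives, formula | False positives, simulation of intercept-only model | t-test on five school means, simulation |
|---|---|---|---|---|
| 0 | 1.00 | 5.0% | 4.9% | 5.1% |
| 0.01 | 1.06 | 6.3% | 6.4% | 5.1% |
| 0.05 | 1.26 | 12.0% | 12.0% | 5.4% |
| 0.10 | 1.50 | 19.1% | 19.4% | 5.3% |

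The simulation used 6,000 trials per setting. Repeat runs gave 6.3 to 6.7%, 11.7 to 12.5% and 18.5 to 18.9% at ICC 0.01, 0.05 and 0.10.

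**Step 3: teachers differ, schools do not (vS = 0).** With vT = 0.3 the true numerator is 0.7. Here s² = (456 + 2.5 × 56 × 0.7)/512 = 1.082, so the reported numerator is 0.433. The SE ratio is √(0.7/0.433) = 1.27 and the false-positive rate 12.3%. Simulations gave 12.1 to 12.9%. A teacher-level paired t-test in the same setting held 5.0%.

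**Step 4: both differ.** In simulation, vS = 0.05 and vT = 0.1 gave 22.5% for the intercept-only model, 16.0% for a teacher-level paired t-test and 4.8% for the test on five school means. A teacher-by-week term therefore removes the teacher part only. The school part remains for any inference beyond these schools.

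**Step 5: what a school-level analysis costs.** The interval on 4 df, relative to a teacher-level interval on 56 df, is √(1 + 10.4 × ICC) × 2.776/2.003 as wide: 1.39 times at ICC 0, 1.46 at 0.01, 1.71 at 0.05 and 1.98 at 0.10. At ICC 0 the whole penalty comes from the degrees of freedom.

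These rates are for the teacher models. The student models have the same gap, with the child-day as residual, but no rate was computed for them.

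**The case against.** The strongest reply is that the intercept-only model is an inference. Describing levels as nested does not rule out random week slopes, and if they were fitted, one sentence would settle the matter. That stands: the documents support saying that no such term is specified, not that none was fitted.

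Second, a reader might infer that the intervals are certainly too narrow. The documents do not support this. With no variation in change the level is nominal, and at an ICC of 0.01 the excess is small.

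Third, a reader might infer that the flaw is one of treating 57 teachers as independent replicates of a school-level delivery. Under the intercept-only reading the replicate is the teacher-day, up to 57 × 10 = 570 of them. So the nearer gap is at teacher level and affects even conclusions confined to these five schools. Delivery was not wholly by school either: school fixed the product, but each teacher received it and decided how to use it.

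Fourth, three products across five schools might seem to make false positives likely. If no product has any effect, product differences add nothing to the variation between schools, and only shared local events can. Product differences argue for unequal effects, and with one product per school the two sources cannot be fully separated. The counterbalancing statement ("The order of product testing was counterbalanced at the school level to minimize contamination and potential timing effects") concerns the three-product sequence that was not carried out. Physical education and recess adjustment removes some shared timetable variation, not all of it.

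Fifth, five schools chosen for the populations they serve are not a sample of schools, so a 4-df interval does not by itself license generalisation. This also stands, and it is why that interval should not become the deciding test.

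**Conclusion.** The point holds in conditional form. The plan specifies no random term for variation in change at teacher or school level. On the natural reading, the week-effect intervals are too narrow whenever such variation exists.

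The size cannot be fixed from the documents. A moderate assumed variance at either level (ICC of change 0.05, or teacher-by-week variance 0.3 of the day variance) more than doubles the nominal 5% error rate, and the two sources add up. This rests on near-equal school sizes, complete five-day weeks, Gaussian outcomes and intercepts only.

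The planned intervals are not safely valid for these five schools without a teacher-by-week term. With that term they would be valid conditional on these schools, and would still say little about others.

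**What to change.** 1. State the random-effects structure of every model.
2. Add a teacher-by-week random term to the teacher and student week-effect models.
3. Beside each week effect, as a sensitivity analysis, report the five school-specific mean changes labelled by product. Add either their mean with a t interval on 4 df, or a school-by-week random term with Kenward-Roger or Satterthwaite degrees of freedom. Name in advance which of the two will be reported, because they will often differ.
4. State that the main intervals are conditional on these five schools, and word conclusions accordingly. Do not let the 4-df test decide.

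This uses data already collected and needs one or two terms and a five-number summary per outcome. The cost is wider intervals. A school-by-week variance from five schools is also poorly estimated: in one balanced five-school simulation with no teacher-by-week variance, it was estimated at zero in 53% of trials at ICC 0.01 and 36% at 0.05. It would also include product differences.

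### The child SB, LPA and MVPA models as described have no classroom-by-day or teacher-by-week term, so week-effect standard errors are too small if any such variance remains after the covariates

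*Combined protocol and SAP*

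**What the plan says.** The Statistical analyses section describes the child models in one sentence: "mixed effects general linear models were estimated with days measured nested within children, children, nested within teachers, and teachers nested within schools". The predictor of interest is the binary baseline/intervention week variable. The activity models adjust for children's "age (years), race, sex, and time in attendance at school", and "all analytic models controlled for school day level factors", namely PE day and recess day. I take attendance time to be entered per day and in all three child models. No random week slope, classroom-by-day effect, cluster-robust standard error or aggregation to class level is mentioned.

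The sections on design and measurement show what children in a class share. Under Study design/procedure, "we collected one baseline week and one intervention week in spring of 2020", and on controls, "The decision was made not to include a comparison group of teachers". Under Sedentary behaviors and Physical Activity, "Each teacher was observed on five school days during baseline and intervention weeks", which I read as five days in each week. In classes above 20, "the first 20 students to arrive to school received an accelerometer each observation day"; in smaller classes every child was monitored.

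For the teacher-log outcomes the section says "Days measured were nested within teachers, and teachers were nested within schools", so there the residual already is the classroom-day.

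**The concern.** With one record per child per day, a day level nested within children is simply the residual. The model treats a day as private to each child, although classmates live through the same one. Lessons, tests, events and teacher routine move a whole class together, and teachers chose when and how long to use the product, so classes may also differ in how they change from one week to the next. None of this is captured by intercepts for child, teacher and school, because those cancel from a within-child week contrast.

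If such variance is left after the covariates, the intervals for the SB, LPA and MVPA week effects are too narrow and the p-values too small. Where the teacher-by-week part is drift unrelated to the product, type I error rises. Where it reflects differing product use, the interval under-covers the average effect. Without a comparison group, ordinary week-to-week drift could be read as a product effect.

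**Working it through.** **The plan's own figure.** The only power figure is a detectable effect of 0.32 with 60 teachers (Sample Size Considerations). A paired t-test at 80% power gives 0.325 with a one-sided 5% alpha and 0.368 two-sided. It concerns teacher minutes and does not bear on the child models, for which no power figure or variance component is given.

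**Inputs from the documents.** 57 classes in five schools; 5 + 5 days; 34 classes with 20 or fewer children, all monitored; 23 classes with mean 24 (SD 1.4), 20 monitored per day.

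**Assumed.** n = 16 children with valid data per class-day, and the variances. Set the individual child-day residual variance, after all covariates, to 1. Let *cd* be the leftover classroom-day variance and *cw* the leftover classroom-week variance, both relative to that 1.

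**Step 1: formula.**

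- True variance of one class's week difference: 2 × [1/(5n) + cd/5 + cw] = (2/(5n)) × (1 + n·cd + 5n·cw).
- Variance the described model reports: (2/(5n)) × (1 + cd + 5cw/9). The pooled residual absorbs *cd*. The *cw* part adds an expected sum of squares of 5cw per child, spread over 9 within-child degrees of freedom.
- Ratio R = (1 + n·cd + 5n·cw)/(1 + cd + 5cw/9).
- Type I error = 2 × [1 − Φ(1.96/√R)].

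**Step 2: results.** The last column comes from a fuller calculation with age, sex, race, attendance, PE and recess as covariates. Its layout is 57 classes in five schools, the smaller ones with 14–20 children, 5.2% opt-out, 90% valid days, PE once a week, recess on 80% of days, and attendance SD of 10 minutes shared by the class-day and 20 minutes individual. Apart from the class counts, the larger-class sizes and the opt-out rate, these are assumptions. It yields 8,857 child-days, 1,067 children and 15.5 children per class-day.

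| cd | cw | R at n = 16 | √R | Type I, formula | Type I, layout |
|---|---|---|---|---|---|
| 0 | 0 | 1.00/1.00 = 1.00 | 1.00 | 5.0% | 5.0% |
| 0.02 | 0 | 1.32/1.02 = 1.29 | 1.14 | 8.5% | 8.4% |
| 0.05 | 0 | 1.80/1.05 = 1.71 | 1.31 | 13.4% | 13.2% |
| 0.10 | 0 | 2.60/1.10 = 2.36 | 1.54 | 20.2% | 19.9% |
| 0 | 0.01 | 1.80/1.006 = 1.79 | 1.34 | 14.3% | 14.0% |
| 0.05 | 0.02 | 3.40/1.061 = 3.20 | 1.79 | 27.4% | 26.9% |

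In the last row of the layout calculation the reported SE is 0.0221 residual SD and the true SE 0.0392, a factor of 0.0392/0.0221 = 1.77.

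**Step 3: credit for the covariates.** Suppose *cd* were 0.10 before adjustment. If PE, recess and attendance removed none, half, four fifths or all of it, 0.10, 0.05, 0.02 or 0 would remain, and type I error would be about 20%, 13%, 8% or 5%.

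**Step 4: does the remedy work?** With a teacher week slope and a classroom-day effect added, and the variance components taken as known, type I error is 5.0% in every row and the SE in the last row is 0.0390. A paired analysis of the 57 class differences was simulated in the last-row setting (4,000 runs, t on 53 degrees of freedom, adjusted for changes in PE, recess and attendance). Child-adjusted class means gave 5.0% with SE 0.039. Restricting to children measured in both weeks gave 5.3–5.8% with SE 0.040.

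**Step 5: what it does not cure.** Adding a school-by-week variance of 0.005 or 0.01 to the last row gives 47% or 56% under the described model, and still 18% or 26% with the added terms.

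**The case against.** The strongest reply is that the text is thin rather than wrong. It gives nesting only, and a random week slope or robust standard errors could have been used without being mentioned. That stands: what is established concerns the models as described, and the first request is to state what was fitted.

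Second, the size is wholly assumed. By the same formula, *cd* of 0.002, 0.005 or 0.01 gives only 5.3%, 5.9% or 6.7%, and nothing in the documents favours the 27% row over these. This also stands, so the figures are illustrative. PE and recess are obvious class-wide influences and are already in the model, but fixed effects remove only what they explain.

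Third, some layout inputs are loose. For instance, 123 opt-outs at 5.2% implies about 2,365 children (123/0.052), while the stated class sizes allow about 34 × 20 + 23 × 24 = 1,232. Measured class size is capped at 20, so the effect is small: about 14.7 rather than 15.5 children per class-day gives 12.7% instead of 13.2% at *cd* = 0.05.

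Fourth, the 5% figure for the enlarged model treats the variance components as known. Estimating them could bring boundary or convergence problems if they are near zero, which is one reason to run the paired check as well.

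Finally, inference limited to the average effect in these 57 classes is defensible where the teacher-by-week variance is differing product use. The documents do not say that this is the target, and it would not excuse omitting the classroom-day term or ignoring drift unrelated to the product.

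**Conclusion.** The concern holds and should be fixed. Followed as written, the nesting gives week-effect standard errors for SB, LPA and MVPA that are too small whenever classroom-by-day or teacher-by-week variance remains after adjustment. The direction is certain under that condition. The magnitude cannot be derived from the documents: it runs from nothing to, in the largest scenario shown, a standard error too small by a factor of about 1.8. The results rest on five days in each week, roughly 16 children per class-day and the assumed variances. The trial team can estimate those variances from data it already holds.

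**What to change.** - State the random effects, standard-error method and degrees of freedom of the child models.
- If the terms are absent, add a random week slope by teacher and a classroom-by-day random effect. Keep all existing levels and covariates (age, race, sex, attendance time, PE day, recess day) and use small-sample degrees of freedom.
- As a check, analyse the 57 paired classroom week differences, adjusted for changes in PE days, recess days and attendance time. Build them from child-adjusted class means or from children measured in both weeks, because the first-arrivals rule can change who is measured. In the assumed layout, 62% of measured children in classes above 20 had unequal numbers of measured days in the two weeks. Unadjusted means also held about 5% when arrival order was random, so the child adjustment guards against a systematic change in who arrives first.
- Secondary and separable: add a random week slope by teacher to the teacher-log models. They need no classroom-day term, but the slope protects against teacher-by-week drift and gives proper coverage for the average effect.
- Report as a limitation that school-by-week drift is not corrected (five schools, one product each, no comparison group), and show the week differences by school.

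The cost is two or three sentences of SAP text and a re-run on existing data. The price is wider intervals: in the largest scenario the reported SE rises from 0.022 to 0.039 residual SD. If the added variances prove near zero, the results stand with better support.
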